HRP-503B – BIOMEDICAL RESEARCH PROTOCOL
(2017-1)

Protocol Title: Song-making In a Group (SING). HIC# 2000026376

Principal Investigator: [name]
[name]
[name]
[name]
[contact]

Version Date: 10/7/2022

Clinicaltrials.gov Registration #: NCT05537428

INSTRUCTIONS

This template is intended to help investigators prepare a protocol that includes all of the necessary information needed by the IRB to determine whether a study meets approval criteria. **Read the following instructions before proceeding:**

1. Use this protocol template for a PI initiated study that includes direct interactions with research subjects. Additional templates for other types of research protocols are available in the system Library.
2. If a section or question does not apply to your research study, type "Not Applicable" underneath.
3. Once completed, upload your protocol in the "Basic Information" screen in IRES IRB system.

SECTION I: RESEARCH PLAN

1. **Statement of Purpose:** *State the scientific aim(s) of the study, or the hypotheses to be tested.*

The overarching aim of the proposed work is to align a promising treatment lead – Musical Intervention (MI) – with a promising mechanistic account of psychosis – Predictive Processing. The R66 phase will investigate the impact of group musical intervention on predictive processing metrics of hallucinations and social dysfunction. Armed with a mechanistic understanding of musical intervention for psychosis, we will be well placed, in the R33 phase, to optimize its administration (Is active participation more effective than passive listening? Does creation of new music help more than performing others' creations?). By tracking the interrelation between symptom mechanisms and MI, we can use those metrics to prospectively assign patients to particular MI.

2. **Probable Duration of Project:** *State the expected duration of the project, including all follow-up and data analysis activities.*

5 years (2 years R61 phase, 3 years R33 Phase)

3. **Background:** *Describe the background information that led to the plan for this project. Provide references to support the expectation of obtaining useful scientific data.*

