In the R61 phase, we will examine the impact of SING on computational behavioral metrics of (Aim 1) Conditioned Hallucinations, (Aim 2) Social Reinforcement Learning, (Aim 3) Language Use, in 50 participants with voice hearing in the context of a psychotic illness. Following a screening visit to determine eligibility, these computerized tasks will be administered behaviorally, and an interview will elicit speech, prior to and following the full SING intervention (in 10 groups of 5 participants, each facilitated by a trained musical interventionist, during the first two years of the project). If SING meaningfully alters these computational task parameters (decision criteria outlined below), we will proceed to the R33 phase, wherein we will recruit a further 200 voice hearing participants with similar diagnoses. These participants will complete the same

tasks deemed mechanistically relevant in the R61 phase, prior to and following randomization to four different conditions (facilitated by an interventionist musician) that will deconstruct the possible active ingredients of SING along two dimensions: Activity and Ownership: (a) SING (n=50, Activity + and Ownership +), participants produce and perform their own song; (b) Karaoke (n=50, Activity + and Ownership -), participants perform karaoke, singing along to others music; (c) Pop Music (n=50, Activity – and Ownership -), participants will listen to popular music chosen by the music interventionists; and (d) Curated Playlists (n=50, Activity -, Ownership +), participants will curate playlists of popular music and listen to them together. This deconstruction will provide insights into the predictive processing framework, as applied to hallucinations and music, specifically, whether changes at higher, a-modal, hierarchical levels, particularly sense of self and active inference, influence precision weighted perceptual and social inferences more so than inactive experiences or experiences that do not engage sense of self.

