		ACTIVE	
		-	+
OWNERSHIP	-	Listening (pop music) n=50	Karaoke (no recording) n=50
	+	Listening (curated playlists) n=50	SING (producing, performing) n=50

Figure 6. R33 Design

R33 Phase: Should we demonstrate a meaningful impact of SING on computational metrics of behavior, we will proceed to use those metrics in the R33 phase where we aim to deconstruct the active ingredients of SING along two key dimensions, Activity (whether engagement with the group is active or passive) and Ownership (creating some novel musical product, or not). Following screening, once participants have been deemed eligible, their behavior on the selected behavioral metrics will be assayed and they will be randomized to an intervention group. Performance on our computational metrics will be balanced across intervention groups prior to commencement of the four interventions (total n=200, n=50 per intervention, 10 groups of 5 participants per intervention):

- (1) **Passive Listening without Ownership** (Activity - / Ownership -, n=50). The group will meet on four occasions, once a week for two hours. The trained facilitator, having procured a playlist of popular music, will spend 15 minutes introducing the session, reminding participants not to sing along and to just sit quietly listening to the music. Next, the facilitator will play music from the playlist through a high-quality speaker at 60-75 decibels for 90 minutes. In the final 15 minutes, the facilitator will summarize the session and dismiss the participants, sharing follow-up music opportunities at the end of the fourth and final session.

- (2) **Passive Listening with Ownership** (Activity - / Ownership +, n=50). The trained facilitator will provide a computer and speaker with the ability to stream songs through many media outlets (i.e., Spotify, YouTube, Google). In the first fifteen minutes, the facilitator will introduce the session, participants are reminded not to sing along and to just sit quietly listening to the music. Next the participants will choose songs that they would like to hear. The list can be edited at any point. For the next 90 mins, the playlist will be played through a high-quality speaker at 60-75 decibels. In the final 15 minutes, the group will be concluded, and the participants will be dismissed. If it is the final session, they will be offered follow-up information about the musical opportunities.

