R33 Power to Detect Effects. Since all participants will perform all tasks; Conditioned Hallucinations, Social Learning and Linguistic Markers, we powered the R33 based on our own preliminary data (on the understanding that any and all of the tasks from the three R61 aims may or may not progress to the R33). Estimated effects for our proposed study of the impact of SING on conditioned hallucinations model parameters are based upon our own data in **Figure 2**. If SING can curtail these group differences – i.e. decrease hallucinating patient responses to the level of non-hallucinating controls, then we would predict the true difference in HGF model parameters pre- versus post-SING would be 0.01 arbitrary units and the within-patient standard deviation of the parameter estimates would be 0.02. We will analyze the model parameter specific to each of the four interventions in a 2x2 design (Activity vs Ownership) using Analysis of Variance, leveraging the added power of within-participants designs. We estimate we will need at least 31 participants to have 80% power to detect a treatment difference at a two-sided 0.05 significance level⁵⁴. We budgeted for 50 unique participants per group to allow for participant drop-out and the detection of smaller effects of SING on conditioned hallucination behavior, social learning and language use.

Robustness and reproducibility (both phases). We have built in a replication study of the effects of SING on conditioned hallucinations, social learning and language use across our R61 and R33 studies (should those metrics satisfy our Go/No-Go criteria). We have chosen to focus on metrics with face and construct validity for psychosis, whose implication in the mechanisms of psychosis have been conceptually replicated across labs in different cities⁵⁷ and countries⁵⁸. Our tasks, analysis code, and data will be made freely available via Yale's ModelDB site. We will optimize and manualize the SING and control interventions in order to prosecute the R61 and R33. Those manuals will be available open access also.

SECTION II: RESEARCH INVOLVING DRUGS, BIOLOGICS, RADIOTRACERS, PLACEBOS AND DEVICES

If this section (or one of its parts, A or B) is not applicable, check off N/A and delete the rest of the section.

- A. RADIOTRACERS N/A
- B. DRUGS/BIOLOGICS N/A
- C. DEVICES N/A

SECTION III: RECRUITMENT/CONSENT AND ASSENT PROCEDURES

1. Targeted Enrollment: *Give the number of subjects.*

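### R33 asks whether creating music beats performing others' music, a SING versus Karaoke comparison, but no term of the planned 2x2 ANOVA tests it unless there is no interaction

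*Combined protocol and SAP*

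**What the plan says.** Section I, 1 (Statement of Purpose) and 3 (Background) give R33 two optimisation questions: whether active participation is more effective than passive listening, and "Does creation of new music help more than performing others' creations".

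Section I, 4 (Research Plan) describes the four arms, 50 participants each:
- SING (Activity+, Ownership+): "participants produce and perform their own song".
- Karaoke (Activity+, Ownership-): "participants perform karaoke, singing along to others music".
- Curated Playlists (Activity-, Ownership+): "participants will curate playlists of popular music and listen to them together".
- Pop Music (Activity-, Ownership-): "participants will listen to popular music chosen by the music interventionists".

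Section I, 13, R33 Phase, glosses the second factor as "Ownership (creating some novel musical product, or not". In its description of the playlist arm, however, "participants are reminded not to sing along and to just sit quietly listening to the music"; their contribution is to choose existing songs.

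The R33 analysis is one sentence under R33 Power to Detect Effects: "We will analyze the model parameter specific to each of the four interventions in a 2x2 design (Activity vs Ownership) using Analysis of Variance". That section names no SING-Karaoke contrast, simple effect or interaction hypothesis. Its sample-size statement is a pre-post calculation for SING.

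**The concern.** The creation question has the null hypothesis SING = Karaoke. None of the three ANOVA terms has that null. The Activity effect compares the active arms with the listening arms. The Ownership effect gives half its weight to two arms in which nobody creates or performs. The interaction asks whether the SING-Karaoke difference equals the Playlist-Pop difference.

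The gloss on Ownership invites a reader to take the Ownership effect as the answer about creation. Among listeners, though, the factor separates choosing songs from not choosing them. Among active participants it separates creating from performing, and Karaoke singers also write a list of songs they want to sing, so some choice is present on both sides. Ownership is therefore manipulated differently at the two levels of Activity, and equal effects cannot be taken for granted.

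At stake is the answer to one of the two questions meant to optimise SING. An effect of choosing a playlist could be mistaken for an effect of creating, or a real effect of creating could be halved before it is tested.

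**Working it through.** **Inputs.** From Section I, 13: 50 per arm in 10 groups of 5, a difference of 0.01, an SD of 0.02, two-sided 0.05, 80% power. The 0.01 is a pre-post change under SING; the plan gives no between-arm difference, so using it as one is an assumption. The 0.02 is called a within-patient SD of the parameter estimates; reading it as the SD of change is also an assumption.

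**The plan's own figure.** n = ((1.960 + 0.842) × 0.02/0.01)² = 31.4, which agrees with the stated 31 for a one-group pre-post comparison. It does not address a comparison between arms.

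**What each term estimates** (arm names stand for mean change, signed so that positive is benefit):
- Ownership = ½[(SING − Karaoke) + (Playlist − Pop)]
- Interaction = (SING − Karaoke) − (Playlist − Pop)
- Hence SING − Karaoke = Ownership + ½ Interaction. Ownership equals the direct contrast only when the interaction is zero.

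**Standard errors** with SD of change 0.02 and 50 independent completers per arm:
- Direct contrast: 0.02 × √(2/50) = 0.0040
- Ownership: 0.02 × √(4 × 0.25/50) = 0.00283
- Interaction: 0.02 × √(4/50) = 0.00566

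**Probability of a significant result** (noncentral t, pooled error, 196 df; the scenarios in rows 1, 2, 4 and 5 were also simulated with 20,000 trials each, with agreement):

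| SING − Karaoke | Playlist − Pop | Ownership | Interaction | Direct contrast |
|---|---|---|---|---|
| 0.01 | 0 | 42% | 42% | 70% |
| 0 | 0.01 | 42% | 42% | 5% |
| 0 | 0.005 | 14% | 14% | 5% |
| 0.01 | 0.01 | 94% | 5% | 70% |
| 0.01 | −0.01 | 5% | 94% | 70% |

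Row 1: the Ownership effect is 0.005, and 0.005/0.00283 = 1.77. The direct contrast gives 0.01/0.0040 = 2.5. Row 3: the Ownership effect is 0.0025, and 0.0025/0.00283 = 0.88.

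**Range for the direct contrast at 0.01:**
- 50 independent completers per arm: 70%. The difference with 80% power is 0.0113.
- 40 completers per arm (assumed; no dropout rate is given): SE = 0.02 × √(2/40) = 0.00447, power 60%.
- Groups of 5 with an assumed ICC of 0.02 to 0.10: variance inflation 1 + 4 × ICC = 1.08 to 1.40, SE 0.00416 to 0.00473. With group-level error (40 groups − 4 = 36 df), power is 65% to 54%.
- 0.02 as the SD of a single measurement, with pre and post uncorrelated: SD of change = 0.02 × √2 = 0.028, power 42%. Ownership power in row 1 is then 24%.

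**The case against.** The strongest reply is that the plan treats creation as the Ownership factor, so the main effect is its intended answer, and that the operational aim of R33 is to separate Activity from Ownership, which a 2x2 ANOVA does. The second half stands: the main effects fit the aim in Section I, 4 and should stay. The first half does not settle the matter, because the Ownership+ listening arm makes no new music. The gloss and the arm then disagree, and that also needs repair.

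Without an interaction the Ownership effect estimates the same quantity with more power (94% against 70%). That stands too. But no-interaction is an assumption, and the plan's own background gives reason to doubt it: the meta-analysis it cites found no significant difference between therapist-selected and patient-selected music, which points towards row 1. The same evidence makes row 2 less likely. Row 2 also takes a playlist effect as large as the one the plan equates with full normalisation under SING; at half that size the figure is 14%.

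Metrics reach R33 only after a change of two standard deviations in R61, so differences may exceed 0.01. At a SING-Karaoke difference of 0.02 with Playlist = Pop, Ownership power is 94%. This eases the loss of power but not the problem of interpretation.

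A reader might infer that the ANOVA is the wrong model, that R33 cannot answer the creation question, or that it carries a 42% false-positive rate. The documents support none of these. The contrast is available from the same fitted model, and nothing rules it out. In row 2 the Ownership null is false, so rejecting it is correct. No section says that such a result will be reported as creation beating performance.

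**Conclusion.** The point holds as a mismatch between a stated question and the analysis named for it. The creation question is SING versus Karaoke, and the planned Ownership effect answers it only under an unstated assumption of no interaction. Under the illustrative assumptions, the cost when only SING and Karaoke differ is 28 points of power (42% against 70%). When only the listening arms differ by 0.01, there is a 42% chance of a significant Ownership effect that could be misread. When there is no interaction, the planned test gains 24 points (94% against 70%).

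These figures rest on a between-arm difference carried over from a pre-post effect, an SD of change of 0.02, 50 completers per arm and independent participants. The mismatch itself rests on none of them. Severity is low to moderate: the main effects remain valid for the Activity and Ownership aim, and the missing contrast needs no new data.

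**What to change.** In Section I, 13, R33 Power to Detect Effects:
- Keep the Activity and Ownership main effects for the aim in the Research Plan.
- Pre-specify one contrast from the same model, mean change in SING minus mean change in Karaoke, with a 95% CI, as the answer to the creation question. Report the interaction beside it.
- State that a significant Ownership effect alone will not be reported as showing that creating helps more than performing.
- State the contrast's power as a range with its assumptions: about 70% at best for 0.01, about 60% with 40 completers per arm, about 54% to 65% for an assumed group ICC of 0.10 to 0.02 with group-level error, and about 42% if 0.02 is the SD of a single measurement and the two measurements are uncorrelated.

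In Section I, 13, R33 Phase, reconcile the definition of Ownership with the playlist arm, which chooses existing songs.

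The cost is wording, one more pre-specified test, and a less favourable stated power for this question. No participants or data are added.

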As in our preliminary data, we will present a visual stimulus as a predictor of tones presented at near-threshold intensities. Over the course of twelve 30-trial blocks, the stimulus pairings will change; early in training, louder tones (75% threshold) will be paired with the visual stimulus, and tone-absent trials will be rare. As the blocks proceed, the number of sub-threshold and tone-absent trials will increase while at-threshold trials will become relatively rare. We will assay the number of tone-absent trials in which participants report perceiving a tone (conditioned hallucination) and tone-absent trials in which they do not report perceiving a tone. We will use a custom-made three-tiered model of perceptual belief formation under uncertainty^{19,20}. Trajectories can be calculated corresponding to the developing prior that tones are predicted by the visual stimulus for each participant. These can be compared pre- and post-SING to establish which processes differ and which change with SING.

[figure not shown]

Figure 5. Preliminary Longitudinal Data.

Data from five P-H- participants (white) and one P-H+ participant (blue) modeled on data obtained at two-time points, separated by 28 and 355 days, respectively. The Conditioned Hallucinations effect and parameter estimates are stable. Data plotted on same vertical axes as **Figs. 1** and **2**. Error bars = 1 SEM.

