R61 Statistical Power: Aims 1-3: Since all participants will perform all studies in Aims 1-3 (Conditioned Hallucinations, Social Learning and Linguistic Markers), we powered our study based on our own preliminary data. Estimated effects for our proposed study of the impact of SING on conditioned hallucinations model parameters are based upon our own data in **Figure 2**. If SING can curtail these group differences – i.e. decrease hallucinating patient responses to the level of non-hallucinating controls, then we would predict the true difference in HGF model parameters pre- versus post-SING would be 0.01 arbitrary units and the within-patient standard deviation of the parameter estimates would be 0.02. We will analyze the model parameter specific to each Aim using paired sample's t-tests, leveraging the added power of within-participant designs. We estimate we will need at least 31 participants to have 80% power to detect a treatment difference at a two-sided 0.05 significance level⁵⁴. We budgeted for 50 unique participants to allow for participant drop-out and the detection of smaller effects of SING on conditioned hallucination behavior, social learning and language use.

Go/No Go Decision: We powered the R61 phase in order to detect complete resolution of conditioned hallucination metrics to the level of non-hallucinating control participants. But we propose a much larger sample of participants in order to be powered to detect smaller changes in conditioned hallucination metrics, social learning and language use. Given standard pharmacotherapies for hallucinations are associated with residual symptoms in 30-50% of participants⁵⁵, it would seem an unfairly high bar to demand complete normalization of a candidate behavioral metric in order for an effect on that metric to be meaningful and solicitous of follow-up investigation. In the clinical trials literature, Jacobson and Truax⁵⁶ determining clinical significance is often used. It is defined as two standard deviations or greater change in the direction of symptomatic improvement following treatment. We propose to adopt this standard for each metric examined in each of Aims 1-3. **Conditioned Hallucination parameters, social learning rates or use of personal pronouns, biological words or negative emotional words change by two standard deviations or more from baseline pre-intervention, then those metrics will proceed to our R33 study. If no metrics meet that standard, we will not proceed with the R33.**

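### R61 measures an uncontrolled change after SING, and the replication promised for R33 names no randomised contrast, so time, retest or interview effects could count as a replicated SING effect

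*Combined protocol and SAP*

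**What the plan says.** **R61.** Item 4 (Research Plan) gives SING to all 50 participants and tests them "prior to and following the full SING intervention". Item 13 adds: "We will analyze the model parameter specific to each Aim using paired sample's t-tests". There is no comparator, yet the Research Plan presents the result as the impact of SING.

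**R33.** Two hundred further participants are randomised to SING, Karaoke, Curated Playlists or Pop Music, with 50 per arm in 10 groups of five. The planned analysis is a 2x2 ANOVA on Activity and Ownership. The R33 power paragraph nevertheless repeats the R61 inputs. The effect is given as "the true difference in HGF model parameters pre- versus post-SING would be 0.01 arbitrary units", with an SD of 0.02 described as within-patient. It also repeats the R61 sample size, "at least 31 participants to have 80% power to detect a treatment difference at a two-sided 0.05 significance level", and then sets 50 per arm to cover drop-out and smaller effects.

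**Replication.** The Robustness paragraph says "We have built in a replication study of the effects of SING on conditioned hallucinations, social learning and language use" across the two phases, for metrics that satisfy Go/No-Go. It attaches no contrast.

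**Go/No-Go.** A metric proceeds to R33 if it changes from baseline by at least two standard deviations.

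**Safeguards.** R61 Aim 1 uses new visual stimuli and different tone frequencies at each visit. R61 Aim 2 uses parallel versions with a different confederate and different deck colours. Retest stability (Figure 5) rests on five P-H- participants retested at about four weeks and one P-H+ participant retested at about a year.

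**Interview.** Under R61 Aim 3, questions about the group experience are asked only after the intervention.

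**The concern.** A pre-post change in one arm contains everything that happens between the two assessments, including any effect of SING. Passage of time and a second exposure to the tasks are obvious candidates. For the language metrics there is a more direct one: the post-intervention interview covers a topic that the first does not, so word-category counts can shift because the questions changed. New stimuli and parallel tasks do nothing about that.

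The retest evidence does not settle the matter. None of the six people in Figure 5 is labelled as having both psychosis and hallucinations, which is the trial population. The one hallucinating person was retested after about a year, not after an interval like that of the four-session intervention.

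If the same pre-post change is then read off the R33 SING arm, any non-specific change recurs and the two phases agree. That agreement would say nothing about SING in particular, although R33 has randomised comparators that could answer the question. The definition matters because the Background reports a meta-analysis with no significant difference between listening and producing music. The SING arm could change while SING minus Pop Music is near zero, and the plan does not say which result would count as replication.

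**Working it through.** **Inputs from the plan.** Difference 0.01; SD 0.02; two-sided alpha 0.05; power 80%; stated n = 31; 50 per arm; groups of five. Drift sizes, intraclass correlation (ICC) and retest correlation are not in the documents and are assumed below.

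**1. The plan's own figure.** For a one-group paired comparison, n = (SD × (z0.975 + z0.80) / difference)² = (0.02 × (1.960 + 0.842) / 0.01)² = 31.4. This reproduces 31, with 0.02 used as the SD of the change. (The exact paired t-test needs 34, and its power at 31 is 76.8%.) A two-arm comparison of change with the same inputs needs 2 × 31.4 = 62.8, so 63 per arm (64 by t-test). The R33 figure is therefore the R61 pre-post calculation carried over.

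**2. Non-specific change, no SING effect.** Let every arm change by k SDs of change. The paired t-test at n = 50 has 49 degrees of freedom and noncentrality k√50. Treating the phases as independent, the chance that both reject is the square of the per-phase figure. This step ignores the Go/No-Go rule.

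| k (assumed) | Change in units | k√50 | Rejects, one phase | Rejects, both phases |
|---|---|---|---|---|
| 0.10 | 0.002 | 0.71 | 11% | 1% |
| 0.25 | 0.005 | 1.77 | 41% | 17% |
| 0.50 | 0.010 | 3.54 | 93% | 87% |

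With 31 completers, k = 0.25 gives 27% and 7%. If 0.02 is instead the SD of a single measurement with independent errors, the SD of change is 0.02 × √2 = 0.0283. A change of 0.005 at n = 50 then gives 23% and 5%.

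**3. Randomised contrast, same scenario.** A change common to all arms cancels in SING minus comparator, so the noncentrality is zero and the test holds its 5% level. Simulation (20,000 runs) gave 5.2% at k = 0.25 and 5.0% at k = 0.5.

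**4. Power of that contrast.** For 50 per arm, noncentrality = (0.01/0.02) × √(50/2) = 2.5, and two-sample t-test power is 70%.
- With an assumed ICC of 0.10, the design effect is 1 + 4 × 0.10 = 1.4, the effective size is 50/1.4 = 35.7 per arm, and power is about 55%.
- If Pop Music gives half the effect, the difference is 0.005, noncentrality is 1.25, and power is about 24% before clustering.
- The uncontrolled paired test at n = 50 has 93%.

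**5. The Go/No-Go rule.** Read as a group mean, with 0.02 as the SD, the bar is 2 × 0.02 = 0.04. The standard error of the mean change is 0.02/√50 = 0.0028, so a drift of 0.005 lies (0.04 − 0.005)/0.0028, or about 12 standard errors, below it. Read per person, with no true change and an assumed retest correlation of 0.5, 2.3% of individuals improve by two SDs. At least one of 50 does so with probability 1 − (1 − 0.02275)^50 = 68%. At a correlation of 0.8 that probability is 4%. The text does not say which reading applies.

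**The case against.** The strongest reply is that the plan has its own filter. Only metrics passing the two-SD rule are carried forward, and if that rule concerns the group mean, modest drift would essentially never reach R33. This stands, and it means that the joint figures in the table cannot be read as the plan's false-replication rate. It does not dispose of the point: the rule is itself an uncontrolled change from baseline, and its level (group or person) is unstated.

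The plan also varies stimuli and task versions. Its stated R33 analysis is a 2x2 ANOVA across randomised arms, and it calls the other arms control interventions. A reader might infer that R33 has no controlled comparison, or that the investigators have committed to presenting two uncontrolled changes as proof. The documents support neither. R33 is randomised; the replication is left undefined, and the only SING effect given a number there is pre-post.

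A reader might also infer that regression to the mean is a main driver, because entry requires daily voices and a hallucination item above 3. Selection is on symptoms, not on model parameters, learning rates or word counts, so it acts only indirectly on the endpoints.

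Finally, SING and Pop Music are opposite corners of the 2x2, so their difference mixes Activity and Ownership. SING could help and still show little advantage if listening helps too. That is a real limit of the example contrast, and a reason to choose and justify one in advance.

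**Conclusion.** The point holds as a defect of definition with a practical consequence. R61 cannot attribute change to SING, and the replication sentence, taken with the R33 power paragraph, most naturally means repeating the same uncontrolled comparison. Under assumed drifts of 0.10 to 0.5 SD of change, a paired test in 50 people rejects 11% to 93% of the time per phase, against about 5% for a randomised contrast. It would go too far to say that the plan carries a 17% risk of false replication: that figure needs an assumed drift of 0.25 SD, full retention, 0.02 as the SD of change, and no Go/No-Go rule. The size of the risk is unknown. That the within-arm comparison cannot separate SING from other sources of change depends on none of these assumptions.

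**What to change.** 1. In the Robustness and reproducibility paragraph, state that any claim that the SING effect is replicated rests on one named, pre-specified randomised contrast of change in R33, adjusted for baseline and allowing for the groups of five. SING minus Pop Music (the cell without Activity or Ownership) is one example. Report the within-arm SING change as descriptive only.
2. In the R33 power paragraph, state power for that contrast, with the assumed ICC and comparator response.
3. In the Research Plan and the R61 parts of item 13, describe the R61 result as change following SING, used to select metrics.

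This needs no new participants or data. For a true between-arm difference of 0.01 with SD of change 0.02, the cost is power of about 70% at 50 per arm, instead of 93% for the paired test. It falls to about 55% at an assumed ICC of 0.10, or about 24% if Pop Music gives half the effect. Baseline adjustment may recover some power, but the documents give no pre-post correlation from which to say how much. The contrast estimates SING over passive listening, not over no music, since every arm receives music.
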